The majority of patients will be transported to University Hospitals Center for Human Genetics to discuss the study and review the informed consent. For patients that are our regular clinic patients, we will see them following a scheduled clinical visit to discuss the study and review the informed consent. At the request of the patient, we will arrange to travel to their community clinic or home to discuss the study and review the informed consent. Informed consent for patients will consist of: 1. The research project goals, risks and benefits will be explained to each patient in person by either myself ([name]) or [name]. 2. Written informed consent will be obtained by either myself ([name]) or [name] from any patient wishing to participate, prior to the initial blood draw is performed. For minors, written informed consent will be obtained from one parent.

Study patients will present to their preferred clinic for 5 office visits. - Visit at beginning of part 1 (initial visit) - Visit at beginning of part 2 - Visit at conclusion of part 2 - Visit at the beginning of part 3 - Visit at the conclusion of part 3

Primary Outcome: - Reduction of baseline Phe levels by 20% OR an increase in dietary Phe tolerance by 20%

Secondary Outcome: - Improved executive functioning and/or quality of life based on BRIEF and PKUQOL surveys as described above.

Initial testing/Part 1: length 4 weeks

Recruited patients will present to clinic for part 1 of the study. After informed consent is obtained, molecular genetic testing will be performed. Testing will include sequence analysis of the PAH gene. This testing is necessary to identify the specific genotypes present in each patient. We expect the majority of this population to be homozygous or heterozygous for the above described splice site mutation. Any patients found not to meet inclusion criteria after PAH gene sequencing will not be able to continue in the study past part I. Genotypes will be grouped and analyzed separately at the conclusion of the study. Patients who do not wish to undergo genetic testing will not be included in the study.

Each patient will also have an initial blood Phe level drawn in the form of a dried blood spot on filter paper card that will be supplied by the testing company. All Phe testing will be performed in a CLIA certified laboratory at The Clinic for Special Children in Strasburg, PA.

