Baseline assessment tools (BRIEF, PKU-QOL) will also be performed at this initial visit. Patients will be given a unique study number by our investigational drug pharmacy and will begin part 1 of the study as described below.

In part 1 of the study, patients will not receive any medication. Each patient will be treated with diet alone. They will maintain a stable, Phe restricted diet (including formula) that is consistent with their diet at the time of enrollment. This will be monitored by food diaries kept for 3 days of each week. Specifically, patients will be expected to keep diaries for the 3 consecutive days leading up to blood draw. Based on these diaries, average weekly Phe intake and Phe tolerance will be calculated and recorded. Patients will also complete a food frequency tool, which will be reviewed at part 1, 2 and 3's initial visit. We will use all of the tools above, plus allow patients regular access to our dietician in order to encourage the maintenance of a stable diet.

Blood Phe concentration will be measured weekly (each Monday) by blood spot cards. Patients will not require weekly clinic visits to have Phe levels drawn. Blood spot cards will be performed at home and then mailed to the reference laboratory. In order to teach and enable patients to become comfortable performing their own blood spots at home, nursing staff (from the DDC clinic) will travel to each patient's house weekly for part 1 of the study (total of 3 home blood spots). For parts 2 and 3 of the study, those patients and families who are able, will perform their own blood spots at home. Those families who remain uncomfortable performing their own blood spots will continue to have their blood spots collected by home nursing.

Initial visit: - Venous blood draw for PAH gene sequencing - Baseline Phe level by dried blood spot card in office - Urine pregnancy testing in females of reproductive age - Executive functioning and quality of life assessment tools (BRIEF, PKU-QOL) given - Baseline diet information collected and recorded.

Average weekly Phe calculated, Phe tolerance calculated. - Food frequency tool completed and reviewed.

Blood Phe values and Phe tolerance from part 1 of the study (on diet treatment alone) will be compared to blood Phe values and Phe tolerance from parts 2 and 3, on low-dose and high-dose treatment.

Part 2: length - 4 weeks

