standard operating procedures and policies of the IRB and with applicable regulatory requirements.

Contact information for BioMarin's Pharmacovigilance Department is as follows: BioMarin Pharmaceutical Inc. [name] [contact] [contact] Email: [contact]

Product Complaints Reporting A product complaint ("Complaint") is any direct, written, electronic, or oral communication of dissatisfaction that alleges deficiencies related to the identity, quality, durability, labeling, purity, stability, appearance, effectiveness, safety, and/or design of a drug product after it is released for distribution. Complaints that simultaneously fall under Adverse Event definitions under this Protocol need only be reported via the Adverse Event reporting procedure set forth in this Protocol. Investigator or designee (Reporter) shall capture the following Complaint information as relates to Saproterin used under this Protocol:

- Date complaint received
- Product Name and Lot Number
- Indicate if the product is available for return to BioMarin for investigation
- Quantity Affected
- Detailed Description of complaint
- Study Protocol Number
- Investigator Name
- Site Contact
- Site Number
- Subject Number
- Name and contact information of the person who is reporting the complaint as well as name and contact information of the complainant. The reporter will be contacted by BioMarin Product Complaint Quality Assurance Department.

Investigator or designee (Reporter) will use his or her best efforts to report Complaints to BioMarin within five days of learning of the Complaint. Investigator or designee will submit the complaint information by email at

[contact] or by fax at [contact]. AE language approved 28 May 15, PC language approved 28 May 2015

Statistical Methods:

We will use student's T-test to compare the mean Phe values for diet treatment alone to both the low and high-dose treatment values. The goal is to determine if there is a significant difference between the groups. Similarly, we will compare calculated phe tolerance from each part of the study.

Power calculations were performed and the following was determined:

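### For families who switch to self-collection, the change of blood-spot collector coincides with the start of drug, so collector and weekly nurse presence are confounded with treatment in the diet-versus-drug Phe comparison

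*Combined protocol and SAP*

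**What the plan says.** All of this is in the combined protocol and SAP, under Proposed Methods unless stated.

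- **Part 1 is off drug** (Initial testing/Part 1): "In part 1 of the study, patients will not receive any medication".
- **Nurses attend the Part 1 home spots.** Nursing staff "will travel to each patient's house weekly for part 1 of the study (total of 3 home blood spots"). The stated aim is to teach families to take their own spots.
- **Collection may pass to the family from Part 2**, when drug starts: "For parts 2 and 3 of the study, those patients and families who are able, will perform their own blood spots at home".
- **Some families do not switch:** "Those families who remain uncomfortable performing their own blood spots will continue to have their blood spots collected by home nursing". No share is given.
- **The comparison spans the switch.** Part 1 values "will be compared to blood Phe values and Phe tolerance from parts 2 and 3, on low-dose and high-dose treatment". Statistical Methods adds: "We will use student's T-test to compare the mean Phe values for diet treatment alone to both the low and high-dose treatment values".
- **Primary Outcome:** response is a 20% fall in Phe from baseline or a 20% rise in Phe tolerance.
- **Office spots** are listed at the initial visits of Parts 1, 2 and 3, all off drug. The final visits of Parts 2 and 3 list no Phe spot.

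The plan does not provide for recording who took each card, for adjusting for it, or for a sensitivity analysis on it.

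**The concern.** There is no placebo period and no concurrent untreated group, so the question of response to drug at all rests on a before-after contrast within patients. Anything else that changes at the same moment is absorbed into the apparent drug effect. For a switching family, two things do change: who takes the spot, and whether a nurse is in the home each week.

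Either could matter. If family-taken spots read systematically higher or lower than nurse-attended ones, the difference enters the estimate. If weekly visits support the stable diet that the plan depends on, losing them as drug starts could raise Phe and hide a response. Randomising dose order does not help, because both dose periods come after the hand-over. Among the spots the plan lists, a switching family has no staff-collected value on drug with which to separate the two influences.

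**Working it through.** **1. Where the switch falls**

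| | Off drug | On drug |
|---|---|---|
| Families who switch | Nurse-attended home spots (Part 1); office spots | Family-taken home spots (Parts 2 and 3) |
| Families who stay with nurses | Nurse-attended home spots (Part 1); office spots | Nurse-taken home spots (Parts 2 and 3) |

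Only the first row is confounded. The second row is not, but those families select themselves.

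**2. The plan's own figure**

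Statistical Methods gives 15 patients for a difference of 200 at alpha 0.05 and 80% power. This cannot be reproduced, because no SD, sidedness or test form is stated. Solving backwards with the noncentral t distribution gives the SD that 15 implies:

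| Test form | Two-sided | One-sided |
|---|---|---|
| Paired, 15 patients (SD of differences) | 257 | 296 |
| Two-sample, 15 per group | 189 | 215 |
| Two-sample, 15 in total (8 and 7) | 127 | 147 |

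I use the two-sided paired case, since each patient contributes both diet and drug values: 200 / 257 = 0.778 SD. The plan gives no unit for 200; umol/L is assumed, as in the eligibility criteria.

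**3. Effect of a shift on the t-test (illustration; the shift is assumed)**

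Mean shift = share of families switching × bias per switching family. Noncentrality = shift / 257 × √n. For a shift of 50 and n = 15: 50 / 257 × 3.873 = 0.75.

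| Mean shift (umol/L) | One way to reach it | Rejection with no drug effect, n = 15 | Same, n = 25 | Power for a true fall of 200 if the shift is upward, n = 15 |
|---|---|---|---|---|
| 0 | none | 5.0% | 5.0% | 80% |
| 12.5 | 25 in half the families | 5.4% | 5.6% | 74.8% |
| 25 | 50 in half | 6.4% | 7.5% | 68.9% |
| 50 | 100 in half, or 50 in all | 10.8% | 15.4% | 55.7% |
| 100 | 100 in all | 29.0% | 46.3% | 29.0% |

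The column for 25 patients uses the enrolment goal. More patients reduce noise but not bias, so the false-positive rate rises.

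**4. Effect on the 20% rule, if Part 1 is the baseline**

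With a proportional collector bias b, a true fall f is counted as response when (1 − f)(1 + b) ≤ 0.80, that is f ≥ 1 − 0.80/(1 + b).

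- b = −5%: 1 − 0.80/0.95 = 15.8%
- b = −10%: 1 − 0.80/0.90 = 11.1%
- b = +5%: 1 − 0.80/1.05 = 23.8%
- b = +10%: 1 − 0.80/1.10 = 27.3%

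I give no false-responder rate. It would need the within-patient SD of percentage change, which the documents do not supply.

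**The case against.** The case against giving this much weight is substantial.

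- **No documented mechanism.** The documents give no collector effect, direction or size. Poorer technique without a consistent direction adds noise, not bias. This stands, and it makes every figure above conditional.
- **Not everyone switches.** A reader might infer that most or all families change collector. The text says only that those who are able will do so, and it keeps nurses for the rest. The point is limited to those who switch.
- **Who took the Part 1 spots is not certain.** That some families continue with nurse collection suggests that nurses took them. The teaching purpose leaves room for families taking some under supervision. If they did, part of the fix is already in place, though nurse presence would still change.
- **The baseline is undefined.** The office spots at the start of Parts 2 and 3 are also called baseline. The 20% rule compares Part 1 with later cards only if Part 1 is the reference.
- **There are safeguards.** One laboratory tests all cards, diaries run through every part, and a food frequency tool and dietician access support a stable diet. These help with assay and adherence, though the diaries are self-reported and none of this standardises collection.
- **Washout may help.** Diaries are kept in washout, and diaries are meant to precede each draw. This suggests off-drug home cards after the hand-over, but none is listed.
- **A before-after contrast has other weaknesses.** True, but this one can be reduced at little cost.

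**Conclusion.** The point holds for families who switch to self-collection. In them, collector and weekly nurse presence are confounded with drug in the diet-versus-drug Phe comparison, and in the Phe part of the response rule if Part 1 is the baseline. The high-versus-standard comparison is largely unaffected because both doses follow the switch. Phe tolerance comes from diaries and depends less on who takes the spot.

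The size is unknown. Under the stated assumptions (two-sided paired test, SD of differences 257, a constant mean shift), the consequence runs from negligible at 12.5 umol/L to serious at 100 umol/L. The upper end needs a large bias in every family, and nothing in the documents shows that.

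A reader might conclude that the diet-versus-drug result will be biased, or biased towards response. The documents support neither: they show an uncontrolled coincidence, not a measured effect, and it could work in either direction. Low severity: a cheap improvement.

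**What to change.** 1. At the nurse visits already planned in Part 1, have the person who will collect in Parts 2 and 3 take the home spot, with the nurse supervising. Families who will rely on nurses use nurses throughout.
2. Record the collector on every card.
3. Add a sensitivity analysis of diet versus drug restricted to cards from the same collector type.

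**Cost.** The nurse's role changes at visits already scheduled, one field is added to the card, and one analysis is added. No extra visits are needed.

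**Downside.** Some Part 1 family cards may be of poorer quality while families learn. With only three home spots in Part 1, a learning effect may remain between early family cards and later, practised ones. A nurse-taken card alongside the first family card limits this.

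**What it leaves.** Switching families still lose the weekly nurse visit when drug starts. The fix aligns the collector, not nurse presence, so that should be stated as a limitation and read together with the diaries.

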Phenylketonuria (PKU) is caused by a deficiency of the enzyme phenylalanine hydroxylase (PAH). PAH is responsible for the rate limiting step in phenylalanine catabolism. This reaction is dependent on tetrahydrobiopterin (BH4). BH4 is a catalytic cofactor for the enzyme PAH. Supplementation with synthetic BH4 (saproterin dihydrochloride or KuvanTm) has been shown to activate residual PAH activity and lower Phe levels in certain patients. It may also have a chaperone effect by binding abnormal PAH protein and decreasing its degradation. Saproterin is an approved oral drug developed to reduce blood Phenylalanine (Phe) levels and increase Phe tolerance in BH4 responsive patients with hyperphenylalaninemia. Data from BH4 loading tests indicate an incidence of BH4 responsiveness of >40% in the general PKU population and >80% in mild PKU patients (6). This therapy is most effective in patients with mild PAH deficiency because they are more likely to have some residual PAH activity. However, there have been a small number of patients with less than 1% residual PAH activity that have been identified as BH4 responsive (2,8).

Certain genotypes have been found to be good predictors of Saproterin responsiveness; however, these correlations are imperfect. Therefore the standard of care is to perform a trial of Saproterin therapy to assess responsiveness in every PAH patient regardless of genotype. Currently this recommendation does not include patients with two null mutations.

The purpose of our study is to determine if Amish patients with PKU show responsiveness after a high dose, prolonged Saproterin trial. Our population of interest has a high frequency of a specific splice site mutation, the 1066-11G>A mutation. This splice site mutation activates a cryptic splice site resulting in an in frame insertion of 9 nucleotides preceding exon 11. This leads to protein conformational changes and abrogation of function. Previous studies of this genotype have indicated <1% residual activity of the PAH enzyme and an insignificant responsiveness to Saproterin. However, in this specific study Phe levels were evaluated only over 24 hours after a single-dose BH4 challenge at the standard dose of 20mg/kg (2).

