Recently, observation in several Amish patients suggests some promise that these patients may be responsive to Saproterin after a longer trial of the medication (Personal comment - [name]). In addition, studies evaluating PAH enzyme activity in these patients, have found evidence that this genotype may need higher cofactor concentrations for optimal enzyme activity and therefore may require a higher dose of Saproterin than the currently recommended 20mg/kg (9). To date, no formal clinical trial has been done.

To answer the question of whether this genotype is responsive to Saproterin at higher doses, over a prolonged period, we propose a randomized clinical trial comparing blood Phe levels in patients treated

with standard-dose Saproterin to those treated with highdose Saproterin . Responsiveness (primary outcome) will be defined as a 20% reduction

in baseline Phe levels on a stable diet or a 20% increase in Phe tolerance while taking Saproterin. As a secondary outcome, executive functioning will be evaluated using the Behavior Rating Inventory of Executive Function (BRIEF), which was previously identified as part of the “uniform assessment method for PKU” (10). Appropriate versions of the BRIEF will be used for each age group. In addition to executive functioning, we will measure quality of life through the previously validated PKU-QOL survey (11).

The results of this study could reveal a new population of Saproterin responsive PKU patients. This could call into question other null mutations of the PAH gene and their responsiveness to Saproterin. This may lead to the investigation of genotypes previously thought to be unresponsive to Saproterin. Further, diet treatment alone has proven to be difficult for the Amish population for cultural and economic reasons and Saproterin may help improve Phe control in responsive patients.

Hypothesis: Based on new clinical information, we hypothesize that if given a prolonged trial of Saproterin at a higher dose, Amish patients with PKU, and more specifically those homozygous for the c.1066-11G>A mutation, will have a significant reduction in Phe levels or an increase in Phe tolerance and/or improvement in executive functioning and quality of life.

PROPOSED METHODS:

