Study numbers will be randomized into “standard-dose Saproterin” or “high-dose Saproterin” groups (treatment group A or treatment group B). The investigational drug pharmacy will provide study patients with their medication in kits, at the beginning of each treatment period. Goal high-dose Saproterin dosing will be 40mg/kg (rounded up to the nearest 500mg), provided in the form of pre-packaged 500mg packets of powder. Labeled dosing on these packets will be covered by the investigational drug pharmacy and unidentifiable to patients. Standard-dose Saproterin will be 20mg/kg (rounded to the nearest 100mg) provided in the form of 100mg tablets. Dosing of the tablets will be unidentifiable to patients. Medication will be given orally once daily.

Initial part 2 visit: after 4 week diet only period - Food diaries collected for the previous 4 weeks (3 per week). Average weekly Phe calculated, Phe tolerance calculated. - Food frequency tool completed and reviewed. - Baseline Phe level drawn by dried blood spot card in office - Urine pregnancy testing in females of reproductive age - Executive functioning and quality of life assessment tools (BRIEF, PKU-QOL) given - Provided with medication kits (high or standard-dose, 4 week supply)

Final part 2 visit: after 4 weeks of treatment - Food diaries collected for the previous 4 weeks (3 per week). Average weekly Phe calculated, Phe tolerance calculated. - Executive functioning and quality of life assessment tools (BRIEF, PKU-QOL) given - Empty medication bottles/packet kits collected from each patient to assess compliance - Review of any potential adverse events

This is the end of part 2. We will then have a 2 week “wash out period” where patients will receive no treatment. The length of this washout period was determined based on the mean elimination half-life of saproterin and previous clinical trials. The mean elimination half-life of saproterin ranges from 3.9 to 17 hours. In previous trials, washout periods have consisted of 7 and 30 days. No efficacy assessments have been performed to differentiate or support one washout period over the other (BioMarin Pharmaceuticals, Inc. Data on file). Based on the elimination range above, we determined that a two week washout period is sufficient. Patients should maintain their steady diet during this time.

Part 3: length – 4 weeks

The cross-over will occur between treatment groups: A \rightarrow B and B \rightarrow A.

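### The randomised contrast, high versus standard dose on blood Phe, has no specified analysis; the only named Phe tests compare each dose with the non-randomised diet period

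*Combined protocol and SAP*

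**What the plan says.** The background text gives a reason for studying dose: this genotype "may require a higher dose of Saproterin than the currently recommended 20mg/kg". It then states the design: "we propose a randomized clinical trial comparing blood Phe levels in patients treated" "with standard-dose Saproterin to those treated with highdose Saproterin". Part 2 carries this out ("Study numbers will be randomized into" a standard-dose or a high-dose group), and Part 3 crosses the groups over after a two-week washout. Only the order of the two doses is randomised. Part 1, diet alone, comes first for everyone.

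The purpose and the primary outcome refer to baseline. The purpose is to learn whether patients "show responsiveness after a high dose, prolonged Saproterin trial", and the Primary Outcome is "Reduction of baseline Phe levels by 20% OR an increase in dietary Phe tolerance by 20"%.

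The Phe analysis appears in two places:

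- Statistical Methods: a Student's t-test to "compare the mean Phe values for diet treatment alone to both the low and high-dose treatment values".
- Part 1: "Blood Phe values and Phe tolerance from part 1 of the study (on diet treatment alone) will be compared to blood Phe values" and tolerance in Parts 2 and 3.

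Statistical Methods adds a general aim of finding a difference between groups, without defining the groups. It compares Phe tolerance part by part. It lists all three conditions (diet and the two doses) only for the survey scores.

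**The concern.** The design and the analysis answer different questions. Randomising and crossing over dose order gives an unconfounded within-patient comparison of the two doses, yet no sentence says that this comparison will be made for blood Phe. If the plan is followed literally, a reader would have to judge dose from two before/after tests. A significant result for one dose and a non-significant result for the other is not evidence that the doses differ.

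The named tests also lack randomised control. Any change in Phe between Part 1 and the later parts enters both of them as apparent drug effect. It could come from diet, from familiarity with home sampling, or from regression to the mean, since entry requires a baseline Phe above 360 umol/L. Diaries and dietician access are meant to limit diet drift but cannot exclude it. A shift common to Parts 2 and 3 cancels from the high-minus-standard difference.

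**Working it through.** **1. Does any wording supply the dose contrast for Phe?**

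| Place | Comparison written | High versus standard on Phe? |
|---|---|---|
| Background | Blood Phe, standard versus high dose | Announced, no analysis |
| Part 1 | Part 1 versus Parts 2 and 3 | No |
| Statistical Methods, t-test | Diet versus each dose | No |
| Statistical Methods, aim | Undefined groups | Ambiguous |
| Statistical Methods, tolerance | Part by part | No: after the crossover, Parts 2 and 3 each contain both doses, so this compares periods |
| Statistical Methods, surveys | Diet, high, standard | Surveys only |

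The finding rests on this table. The figures below only illustrate the consequences.

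**2. The plan's own figure.** Statistical Methods gives 15 patients for a difference of 200 (no unit, no named contrast), alpha 0.05 and 80% power, with enrolment of up to 25. No SD is stated, so 15 cannot be reproduced, only back-solved. Using the non-central t distribution:

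- Paired, two-sided: standardised difference 0.778, so SD of differences = 200/0.778 = 257.
- Paired, one-sided: 0.675, so 200/0.675 = 296.
- Unpaired, 15 per condition: SD 189 per condition. The paired-difference SD is SD × √(2(1−ρ)), which is 189 at ρ = 0.5 and 267 at ρ = 0.
- Unpaired, 7 and 8: SD 127 per condition, so a paired-difference SD of 127 to 180.

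The base case is 257; the compatible range is 127 to 296.

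**3. Can two diet tests stand in for a dose test?** Simulated trials gave each patient a diet, a standard-dose and a high-dose value. The SD per condition was (paired SD)/√2, the diet value was shared by both tests, and all tests were paired and two-sided at 0.05. Both doses truly lower Phe by 200, so the doses do not differ. Share of trials with exactly one dose significant against diet:

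| Paired SD | n = 15 | n = 25 |
|---|---|---|
| 127 | 0.0% | – |
| 180 | 3.6% | 0.1% |
| 189 | 5.3% | – |
| 257 | 23.5% | 6.2% |
| 267 | 25.6% | – |
| 296 | 30.6% | 13.8% |

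A direct high-versus-standard test is significant in 5% of trials throughout. At SD 257 and n = 15, high significant and standard not occurs in about 12%. The matching one-direction rate for the direct test is 2.5%.

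**4. What does drift do?** Assume no drug effect but Phe 100 lower in both treatment parts than in Part 1. The 100 is hypothetical.

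| Setting | Each diet test significant | At least one |
|---|---|---|
| n = 15, SD 257 | 29% | 44% |
| n = 15, SD 296 | 23% | 36% |
| n = 15, SD 180 | 52% | 69% |
| n = 25, SD 257 | 46% | 63% |

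A fall of 50 gives 11% per test at n = 15 and SD 257. The direct test stays at 5%. More patients make the diet tests more likely to pick up the drift.

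**5. What would the direct contrast deliver?** Let D be a patient's high-minus-standard difference. Averaging the mean of D over the two sequences removes the period effect, with SE = (SD/2)·√(1/n₁ + 1/n₂) on n−2 degrees of freedom. At SD 257:

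- n = 15 (7/8): SE = 128.5 × 0.5175 = 66.5; 95% half-width = 2.160 × 66.5 = 144; power for a difference of 100 is 29%.
- n = 25 (12/13): SE = 128.5 × 0.4003 = 51.4; half-width = 2.069 × 51.4 = 106; power for 100 is 46%.

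**The case against.** The strongest reply is that dose-versus-diet is the main question. The purpose, the hypothesis and the primary outcome all refer to baseline, the named tests match them, and nothing says that superiority of high dose will be claimed. That stands as a reason to keep the diet tests. It does not account for the randomised dose comparison that the background announces.

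A second reply is that the intention can be inferred. Part 2 uses the word groups for the two dose arms, and the survey sentence counts diet as a third, so the stated aim could cover high versus standard. This is a fair reading of intent. It still leaves the estimate, the pairing, the handling of period and the summary of the weekly values unspecified.

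Third, the figures depend on assumptions. The SD is back-solved, the drift has no source, and pairing is assumed because the plan says only Student's t-test. This is correct, and the first illustration runs from about 0% to 31%, so it cannot establish how serious the gap is in this trial.

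Fourth, the direct contrast has limits of its own. It is not immune to carryover, which the simulation set to zero. Two weeks is 336/17, or about 20, of the longest half-life that Part 2 quotes, but Part 2 also says that no efficacy data favour one washout length over another. In addition, high dose is given as powder packets and standard dose as tablets, so the contrast is between regimens as supplied rather than pure dose. Both limits should be stated in the plan; neither removes the need for the contrast.

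**Conclusion.** The concern holds. The protocol announces a randomised comparison of blood Phe on two doses and randomises dose order to support it, but specifies only non-randomised comparisons with diet. This follows from the text alone and needs no assumption about variability.

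The practical size is uncertain because no SD is given. With the back-solved SD of 257 and 15 patients, two equally effective doses would look different against diet in about 23% of trials, compared with 5% for a direct test. A post-Part-1 fall of 100 would make each diet test significant in 29% of trials without any drug effect. These rates assume paired tests, the same SD for every contrast and no carryover.

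The plan should be changed, but the gap does not undo the trial: the responsiveness analysis remains usable as a before/after comparison.

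**What to change.** The core change in Statistical Methods is to pre-specify the within-patient high-minus-standard difference in on-treatment blood Phe, with 95% CI and p-value, from a paired crossover analysis adjusted for period (Part 2 or Part 3). Name one summary of the weekly values and apply it to both doses.

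Then, in the same section:

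- Give the same contrast for Phe tolerance, by dose rather than by part.
- For the 20% responder outcome, report patients responding on high only, standard only, both and neither, with an exact paired test. That test uses only discordant patients and will be weak at this size, so the table matters more than the p-value.
- Keep dose-versus-diet as the responsiveness analysis and label it a non-randomised before/after comparison.
- Use the post-washout Phe at the initial Part 3 visit as a drift check, noting that it is a single value and could also reflect carryover.
- State the no-carryover assumption and the difference in formulation.

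The cost is wording and a little more analysis, with no new visits, samples or patients. Part 3 keeps Phe values from the researchers until the study ends, so the change can be made before any result is seen. The drawback is imprecision: under the assumed SD the interval is about ±144 with 15 patients and ±106 with 25. The report should therefore lead with the estimate and interval, and should not read a non-significant result as equal effect.
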